#### **11.4 Recording of Data**

A CRF is required and must be completed for each subject by qualified and authorized personnel. All data on the CRF must reflect the corresponding source document, except when a section of the CRF itself is used as the source document. Any correction to entries made on the CRF must be documented in a valid audit trail where the correction is dated, the individual making the correct is identified, the reason for the change is stated, and the original data are not obscured. Only data required by the protocol for the purposes of the study should be collected.

The investigator must sign each CRF. The investigator will report the CRFs to the sponsor and retain a copy of the CRFs.

#### **11.5 Identification of Source Data**

All data to be recorded on the CRF must reflect the corresponding source documents. For the following item(s), the data recorded directly on the CRF are to be considered source data:

- Study treatment compliance (eg, the reason for dose reduction).
- Discontinuation information.
- Sampling date and time for drug concentration.
- Sampling date and time for the clinical laboratory test.
- Comments and other information on AEs (eg, severity, relationship to study treatment, outcome).

#### **11.6 Retention of Records**

The circumstances of completion or termination of the study notwithstanding, the investigator is responsible for retaining all study documents, including but not limited to the

protocol, copies of CRFs, the Investigator's Brochure, and regulatory agency registration documents (eg, Form FDA 1572, ICFs, and IRB/IEC correspondence). The site should plan to retain study documents, as directed by the sponsor, for at least 2 years after the last approval of a marketing application in an ICH region and until there are no pending or contemplated marketing applications in an ICH region or at least 3 years have elapsed since the formal discontinuation of clinical development of the investigational product.

It is requested that at the completion of the required retention period, or should the investigator retire or relocate, the investigator contact the sponsor, allowing the sponsor the option of permanently retaining the study records.

## **11.7 Auditing Procedures and Inspection**

In addition to routine monitoring procedures, the sponsor's Clinical Quality Assurance department conducts audits of clinical research activities in accordance with the sponsor's SOPs to evaluate compliance with the principles of ICH GCP and all applicable local regulations. If a government regulatory authority requests an inspection during the study or after its completion, the investigator must inform the sponsor immediately.

## **11.8 Handling of Study Drug**

All study drug will be supplied to the principal investigator (or a designated pharmacist) by the sponsor. Drug supplies must be kept in an appropriate secure area (eg, locked cabinet) and stored according to the conditions specified on the drug labels. The investigator (or a designated pharmacist) must maintain an accurate record of the shipment and dispensing of the study drug in a drug accountability ledger, a copy of which must be given to the sponsor at the end of the study. An accurate record of the date and amount of study drug dispensed to each subject must be available for inspection at any time. The CRA will visit the site and review these documents along with all other study conduct documents at appropriate intervals once study drug has been received by the site.

All drug supplies are to be used only for this study and not for any other purpose. The investigator (or site personnel) must not destroy any drug labels or any partly used or unused drug supply before approval to do so by the sponsor. At the conclusion of the study and as appropriate during the study, the investigator (or a designated pharmacist) will return all used and unused drug containers, drug labels, and a copy of the completed drug disposition form to the sponsor's CRA or, when approval is given by the sponsor, will destroy supplies and containers at the site.

## **11.9 Publication of Results**

All manuscripts, abstracts, or other modes of presentation arising from the results of the study must be reviewed and approved in writing by the sponsor in advance of submission pursuant to the terms and conditions set forth in the executed Clinical Trial Agreement between the sponsor/CRO and the institution/investigator. The review is aimed at protecting

---

the sponsor's proprietary information existing either at the date of the commencement of the study or generated during the study.

The detailed obligations regarding the publication of any data, material results, or other information generated or created in relation to the study shall be set out in the agreement between each investigator and the sponsor or CRO, as appropriate.

## **11.10 Disclosure and Confidentiality**

The contents of this protocol and any amendments and results obtained during the study should be kept confidential by the investigator, the investigator's staff, and the IRB/IEC and will not be disclosed in whole or in part to others, or used for any purpose other than reviewing or performing the study, without the written consent of the sponsor. No data collected as part of this study will be used in any written work, including publications, without the written consent of the sponsor. These obligations of confidentiality and non-use shall in no way diminish such obligations as set forth in either the Confidentiality Agreement or Clinical Trial Agreement executed between the sponsor/CRO and the institution/investigator.

All persons assisting in the performance of this study must be bound by the obligations of confidentiality and non-use set forth in either the Confidentiality Agreement or Clinical Trial Agreement executed between the institution/investigator and the sponsor/CRO.

## **11.11 Discontinuation of Study**

The sponsor reserves the right to discontinue the study for medical reasons or any other reason at any time. If a study is prematurely terminated or suspended, the sponsor will promptly inform the investigators/institutions and regulatory authorities of the termination or suspension and the reason(s) for the termination or suspension. The IRB/IEC will also be informed promptly and provided the reason(s) for the termination or suspension by the sponsor or by the investigator/institution, as specified by the applicable regulatory requirement(s).

The investigator reserves the right to discontinue the study should his/her judgment so dictate. If the investigator terminates or suspends a study without prior agreement of the sponsor, the investigator should inform the institution where applicable, and the investigator/institution should promptly inform the sponsor and the IRB/IEC and provide the sponsor and the IRB/IEC with a detailed written explanation of the termination or suspension. Study records must be retained as noted above.

## **11.12 Subject Insurance and Indemnity**

The sponsor will provide insurance for any subjects participating in the study in accordance with all applicable laws and regulations.

## 12 APPENDICES

## **Appendix 1      Overview of RECIST v1.1 for Evaluation of Tumors Response**

Tumor response assessments in this clinical study will use RECIST v1.1 guidelines based on the article by [Eisenhauer, et al., 2009](#), entitled “New response evaluation criteria in solid tumours: Revised RECIST guideline (version 1.1),” with the exception that chest disease may not be followed using chest x-ray and must be assessed with CT. This appendix contains an overview of the RECIST v1.1 guidelines.

### **Baseline Tumor Assessment**

Subjects are required to have measurable disease, defined as the presence of at least 1 measurable lesion, to be eligible for entry into the study. Measurable and nonmeasurable lesions are defined as:

#### **Measurable lesions:**

Tumor lesions: Must be accurately measured in at least 1 dimension (longest diameter in the plane of measurement is to be recorded) with a minimum size of:

10 mm by CT scan (CT scan slice thickness no greater than 5 mm)

10 mm caliper measurement by clinical exam (lesions, which cannot be accurately measured with calipers, should be recorded as nonmeasurable)

Malignant lymph nodes: To be considered pathologically enlarged and measurable, a lymph node must be >15 mm in short axis when assessed by CT scan (CT scan slice thickness recommended to be no greater than 5 mm). At baseline and in follow-up, only the short axis will be measured and followed.

MRI may be substituted for contrast enhanced CT for some sites, but not lung. The minimum size for measurability is the same as for CT (10 mm) as long as the scans are performed with slice thickness of 5 mm and no gap. In the event the MRI is performed with thicker slices, the size of a measurable lesion at baseline should be 2 times the slice thickness. In the event there are interslice gaps, this also needs to be considered in determining the size of measurable lesions at baseline.

Lytic bone lesions or mixed lytic-blastic lesions, with identifiable soft tissue components, that can be evaluated by cross-sectional imaging techniques such as CT or MRI can be considered as measurable lesions if the soft tissue component meets the definition of measurability.

A lesion located in a previously irradiated area, or in an area previously subjected to any locoregional therapy, will be considered measurable only if there has been a documented increase in lesion size subsequent to prior treatment but before study entry.

**Clinical lesions:** Clinical lesions will only be considered measurable when they are superficial and >10 mm diameter as assessed using calipers (eg, skin nodules). For the case of skin lesions, documentation by color photography including a ruler to estimate the size of the lesion is suggested. When lesions can be evaluated by both clinical exam and imaging, imaging evaluation should be undertaken since it is more objective and may also be reviewed at the end of the study.

**Nonmeasurable lesions:** All other lesions, including small lesions (longest diameter < 10 mm or pathological lymph nodes with a short axis of  $\geq$  10 mm to < 15 mm short axis), lesions that cannot be accurately measured with calipers, and truly nonmeasurable lesions: leptomeningeal disease, ascites, pleural or pericardial effusion, inflammatory breast disease, lymphangitic involvement of skin or lung, abdominal masses/abdominal organomegaly identified by PE that is not measurable by reproducible imaging techniques. Lymph nodes with a short axis <10 mm are considered nonpathological and should not be recorded or followed.

Simple cysts (cystic lesions) will not be considered malignant, and will be neither measurable nor nonmeasurable. Cystic lesions believed to be metastases may be considered measurable if they meet the general definition of measurability, but noncystic lesions are preferred as target lesions.

All baseline tumor evaluations should be performed as closely as possible to the start of treatment and never more than 4 weeks before the first dose of study treatment.

## **Methods of Tumor Measurement**

The same imaging modality and the same technique (including use or nonuse of oral and IV contrast) should be used to characterize each identified and reported lesion at Baseline/Screening and at reassessment time points during the study. All measurements should be taken and recorded in metric notation, using calipers if clinically assessed.

Computed tomography and MRI are the best currently available and reproducible methods to measure target lesions selected for response assessment. Computed tomography should be performed with slices of 5 mm or less in thickness (as a general rule, lesion diameter should be no less than double the slice thickness). This applies to tumors of the chest, abdomen, and pelvis. Magnetic resonance imaging is also acceptable in certain conditions (eg, for body scans). A CT of the chest without contrast is preferred over MRI.

Bone scans, positron emission tomography (PET) scan, or plain films are not sufficient to measure bone lesions and document objective response but may be used to confirm the presence or disappearance of such lesions. Bone scans should be performed using  $^{99}\text{m}$ -technetium-labeled polyphosphonate scintigraphy, whole body bone MRI, or  $^{18}\text{F}$ -NaF-PET.

Chest x-rays should not be used for baseline assessment of the chest or for follow-up of known lesions. Chest CT should be used.

Ultrasound should not be used to measure tumor lesions.

Endoscopy and laparoscopy should not be used to measure tumor lesions.

### **Documentation of "Target" and "Nontarget" Lesions**

Lesions are evaluated and classified at Baseline as either target or nontarget and all are then followed throughout the study.

#### *Target Lesions:*

Target lesions are all measurable lesions up to a maximum of 2 lesions per organ and 5 lesions in total, representative of all involved organs. Target lesions should be selected on the basis of their size (those with the longest diameters) and their suitability for accurate repeated measurements.

The short axis ( $\geq 15$  mm) of any lymph nodes selected as target lesions at Baseline will be measured and recorded at each evaluation time point, even if the nodes become nonpathological (short axis  $< 10$  mm).

The sum of the diameters of all target lesions (longest for nonnodal lesions, short axis for nodal lesions) will be calculated at Baseline and reported as the baseline sum diameter. This baseline sum of diameters will be used as the reference by which to characterize objective tumor response.

#### *Target Lesions Too Small To Measure:*

Lesions that become too small to measure during treatment should be assigned a default measurement of either 0 mm (if the investigator believes the lesion has disappeared) or 5 mm (if the lesion is believed to be present and is faintly visible).

#### *Target Lesions That Split or Coalesce:*

If a nonnodal target lesion fragments during treatment, the longest diameters of each fragment should be added together to calculate the total sum for that lesion. When lesions coalesce, a plane between them may be maintained that would aid in obtaining maximal diameter measurements for each individual lesion. If the lesions are no longer separable, the vector of the longest diameter in this instance should be the maximal longest diameter for the coalesced lesion.

#### *Nontarget Lesions:*

All other lesions (or sites of disease) should be identified as nontarget lesions and should also be recorded at Baseline. Measurements of these lesions are not required, but the presence or absence of each should be noted throughout Follow-up.

*New Lesions:*

The finding of a new lesion should be unequivocal (ie, not attributable to a change in scanning technique or imaging modality, and not thought to represent something other than a tumor). If a possible new lesion is equivocal, treatment and radiographic evaluation should continue per this protocol until confirmation of PD or until additional scans confirm the presence of a new lesion. In such a case, the date of progression will be the date of the initial scan.

A lesion identified on a Follow-up study of an anatomical location not studied as Baseline will be considered a new lesion.

Scanning with fluorodeoxyglucose positron emission tomography (FDG-PET) may be employed as a complement to CT scanning in the assessment of PD. A negative FDG-PET scan at Baseline with a positive scan during the study will be evidence of PD. If there is no FDG-PET scan at Baseline and a positive FDG-PET scan during the study, it will be considered evidence of PD if the positive FDG-PET corresponds to a new site of disease confirmed by CT scan. A positive postbaseline FDG-PET result corresponding to a preexisting site of disease with no radiographic evidence of progression will not be considered evidence of PD.

**Evaluation of Response for an Individual Assessment Time Point**

To determine tumor response, the sum of all target lesions is calculated at Baseline and at each subsequent assessment time point (ie, every 6 weeks until progression in this study). Each response parameter (target, nontarget, and new lesions) will be reported independently at each radiographic reading as shown below in Table 1 for target lesions and [Table 2](#) for nontarget lesions. The investigator will then make a determination of OR for each assessment time point based on a composite evaluation of target, nontarget, and new lesions, as shown in [Table 3](#).

**Appendix 1 - Table 1 Evaluation of Target Lesions**

Complete Response (CR)	Disappearance of all target lesions. All pathological lymph nodes (whether target or nontarget) must have a reduction in their short axis to <10 mm.
Partial Response (PR)	At least a 30% decrease in the sum of the longest diameter (LD) of target lesions, taking as reference the Baseline sum diameters
Progressive Disease (PD)	At least a 20% increase in the sum of the LD of target lesions, taking as reference the smallest sum LD recorded at Baseline or during treatment. The sum must also have an absolute increase of $\geq 5$ mm.
Stable Disease (SD)	Neither sufficient shrinkage to qualify for PR nor sufficient increase to qualify for PD, taking as reference the smallest sum LD since the treatment started
Not Evaluable (NE)	No imaging/measurement done at all or only on a subset of lesions at a particular time point; a target lesion at Baseline that is subsequently not measured or that is unable to be evaluated. Includes scans that are not performed at a specified time point to evaluate the target lesion(s).

**Appendix 1 - Table 2 Evaluation of Nontarget Lesions**

Complete Response (CR)	Disappearance of all nontarget lesions. All lymph nodes <10 mm (short axis)
Non-CR/Non-PD	Persistence of 1 or more nontarget lesion(s)
Progressive Disease (PD)	Unequivocal progression (substantial worsening in nontarget disease such that overall tumor burden has increased sufficiently to warrant discontinuation of therapy); unequivocal progression of existing nontarget lesions a
Not Evaluable (NE)	A nontarget lesion at Baseline that is subsequently not measured or that is unable to be evaluated

a: Although a clear progression of "nontarget" lesions only is exceptional, in such circumstances, the opinion of the site radiologist should prevail.

**Appendix 1 - Table 3 Overall Response at Each Assessment Time Point for Subjects with Target ( $\pm$  Nontarget) Disease**

Target Lesions	Nontarget Lesions	New Lesions	Overall Response
CR	CR	No	CR
CR	Non-CR/Non-PD	No	PR
CR	Not evaluated	No	PR
PR	Non-PD or not all evaluated	No	PR
SD	Non-PD or not all evaluated	No	SD
Not all evaluated	Non-PD	No	NE
PD	Any	Yes or No	PD
Any	PD	Yes or No	PD
Any	Any	Yes	PD

CR = complete response, NE = not evaluable, PD = disease progression, PR = partial response, SD = stable disease.

Subjects with a global deterioration of health status requiring discontinuation of treatment without objective evidence of PD at that time point assessment should be classified as having "symptomatic deterioration." Every effort should be made to document objective progression after discontinuation of treatment.

In some circumstances, it may be difficult to distinguish residual disease from normal tissue. When the evaluation of CR depends on this determination, it is recommended that the residual lesion be investigated (fine needle aspirate/biopsy) before assigning a status of CR.

**Evaluation of Best Overall Response (BOR) and Confirmation of Response**

The best overall response is the best response recorded from the start of the treatment until disease progression/recurrence (taking as reference for PD the smallest measurements [nadir] recorded since the treatment started). In general, the subject's best response assignment will

depend on the achievement of both measurement and confirmation criteria as shown in Table 4.

Confirmation: To be assigned a BOR of PR or CR, changes in tumor measurements must be confirmed by repeat assessments that should be performed no less than 4 weeks after the criteria for response are first met. In this study, a bone scan should be done within 1 week after the CR confirmatory scanning time point to exclude new bone metastases.

- The main goal of confirmation of the PR or CR objective response is to avoid overestimating the response rate.
- In the case of SD, follow-up measurements must have met the SD criteria at least once after study entry at a minimum interval of 5 weeks for this protocol.

#### Appendix 1 - Table 4 Best Overall Response With Confirmation

Unconfirmed response (First Time Point)	Confirmatory Response (Subsequent Time Point)	Best Overall Response of:
CR	CR	CR
CR	PR	SD, PD or PR a
CR	SD	SD or PD b
CR	PD	SD or PD b
CR	NE	SD or NE c
PR	CR	PR
PR	PR	PR
PR	SD	SD
PR	PD	SD b
PR	NE	SD c
NE	NE	NE

BL = baseline, CR = complete response, NE = not evaluable, PD = disease progression, PR = partial response, SD = stable disease.

a: If a CR is truly met at the first time point, then any reappearance of disease seen at a subsequent time point (including disease meeting PR criteria relative to BL) makes the disease PD at that time point.

b: Classify response as SD, provided that confirmatory scan a minimum of 5 weeks later is still "SD." Otherwise, response will be classified as PD.

c: Classify response as SD, provided that confirmatory scan a minimum of 5 weeks later is still "SD." Otherwise, response will be classified as NE.

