##### 9.7.1.1.2 SECONDARY ENDPOINTS

The secondary efficacy endpoints are:

- PFS based on investigator assessment – defined as the time from date of first dose of study drug to date of first documentation of disease progression or death, whichever occurs first.
- OS – defined as the time from the date of first dose of study drug until date of death from any cause.

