##### 9.7.1.1.3 EXPLORATORY ENDPOINTS

The exploratory endpoints are:

- ORR based on IIR assessment.
- PFS based on IIR assessment.
- CBR is the proportion of subjects who have a BOR of CR or PR or durable SD. Stable disease must be achieved at  $\geq 23$  weeks after first lenvatinib administration to

be considered durable SD. The CBR will be determined based on both investigator and IIR assessments.

- DCR is the proportion of subjects who have a BOR of CR, PR, or SD. The DCR will be determined based on both investigator and IIR assessments.
- DOR is defined as the time from the date that the criteria are met for CR or PR (whichever is recorded first) to the date that PD is objectively documented or death, whichever occurs first. The DOR will be determined based on both investigator and IIR assessments.

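### Appendix 1 Table 4, footnote b cannot return SD when the confirmatory scan is PD, so it contradicts the SD printed for PR then PD; exploratory DCR, and sometimes CBR, can shift

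*Protocol*

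**What the plan says.** Appendix 1 of the protocol makes Table 4 the rule for BOR: a subject's assignment will "depend on the achievement of both measurement and confirmation criteria as shown in Table 4". The table pairs an unconfirmed response at the first time point with the confirmatory response at the subsequent time point. Footnote b is attached to three rows:

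- CR then SD: the cell prints SD or PD.
- CR then PD: the cell prints SD or PD.
- PR then PD: the cell prints SD alone.

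The footnote reads "Classify response as SD, provided that confirmatory scan a minimum of 5 weeks later is still" SD, and then "Otherwise, response will be classified as PD".

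The text above the table sets the window and a separate test for SD. On the window: "The best overall response is the best response recorded from the start of the treatment until disease progression/recurrence". On SD: "follow-up measurements must have met the SD criteria at least once after study entry at a minimum interval of 5 weeks for this protocol". Study entry is not defined there.

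Two exploratory endpoints use the SD class (Section 9.7.1.1.3). For one, "DCR is the proportion of subjects who have a BOR of CR, PR, or SD". The other, CBR, counts CR, PR and durable SD, where SD must be reached at 23 or more "weeks after first lenvatinib administration". Both are derived from investigator and from independent imaging review, and both get a Clopper–Pearson interval without a test (Section 9.7.1.6.3).

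**The concern.** A rule that assigns an endpoint category should give one answer per subject. Here the footnote's condition looks forward to the confirmatory scan, yet in two of its three rows that scan has already been fixed as PD. The cell and its own footnote therefore give different classes for the same subject in the PR-then-PD row. Two programmers working from this table could derive different BORs from identical data.

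At stake is the split of non-responders between SD and PD: the BOR tabulation, DCR and, for late unconfirmed responses, CBR. It is better settled before anyone can see which reading favours the result.

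**Working it through.** **1. The footnote applied to each row that carries it**

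| First scan | Confirmatory scan | Printed BOR | Footnote b returns | Result |
|---|---|---|---|---|
| CR | SD | SD or PD | SD, if at least 5 weeks later | works |
| CR | PD | SD or PD | PD always | SD option unreachable |
| PR | PD | SD | PD always | contradiction |

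A scan after the PD cannot rescue SD, because the BOR window closes at progression.

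**2. Is the 5-week interval the obstacle?**

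Scans are due every 8 weeks, within the 8th week, from first dose (Section 9.5.1.2.1; Table 5, footnote v). Take Day 1 as first dose.

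- First scan: days 50–56, which is 49–55 days or 7.0–7.9 weeks after first dose. The minimum is 5 × 7 = 35 days, so it is met.
- Second scan: days 106–112, which is 105–111 days or 15.0–15.9 weeks after first dose.
- Gap between them: 106 − 56 = 50 to 112 − 50 = 62 days, again above 35.

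For on-schedule scans the interval is always met. What cannot be met is the demand that the confirmatory scan is still SD.

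**3. The footnote against the SD test in the text**

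The interval is counted from first dose, with scans at weeks 8, 16 and 24. Strict means that a scan was itself SD; Appendix 1, Table 1 defines SD as falling short of PR, so a PR scan is not strictly SD.

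| Sequence | Text test, strict | Text test, SD or better | Footnote b |
|---|---|---|---|
| SD, PR, PD | met | met | PD |
| PR, PD | not met | met | PD |
| CR, PD | not met | met | PD |

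The first sequence conflicts with the text on its strictest wording. The other two conflict only on the SD-or-better reading. The SD printed in the PR-then-PD cell needs that reading too.

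**4. What does not move**

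The design figures reproduce. With X1 ~ Bin(16, p) and X2 ~ Bin(15, p):

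P(reject) = sum over x = 2 to 16 of P(X1 = x) × P(X2 ≥ max(0, 6 − x)); P(stop early) = P(X1 ≤ 1).

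- p = 0.08: type I error 0.0319, early stopping 0.6299.
- p = 0.25: power 0.8053, early stopping 0.0635.

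All four match Sections 9.7.2 and 9.7.3. SD and PD are both non-responses, so no responder count changes. PFS is "defined as the time from date of first dose of study drug to date of first documentation of disease progression or death", so it uses the progression date, not BOR. DOR concerns responders only.

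**5. What can move**

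- DCR: with 31 subjects in the Full Analysis Set, 1/31 = 3.2 points for one affected subject, 2/31 = 6.5 for two, 3/31 = 9.7 for three.
- The DCR interval: comparing k with k − 1 out of 31 for every k from 1 to 31, each Clopper–Pearson 95% limit shifts by between 0.08 and 5.48 points.
- CBR: for an unconfirmed response on the first scan, PD at 15.0–15.9 weeks comes before the 23-week mark, so CBR is unchanged. For a first PR at week 24 (days 162–168; 161/7 = 23.0 to 167/7 = 23.9 weeks after first dose) and PD at week 32, the printed cell gives SD at or beyond 23 weeks, which can count as durable SD. The footnote gives PD, which cannot.

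**The case against.** The strongest reply is that this is one mismatched cell in an appendix. The CR-then-PD cell prints SD or PD, so a footnote that returns PD gives a permitted answer. That stands: the row is not contradicted, only left with an option that nobody can reach.

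Second, the conflict with the text is not shown for a subject who goes straight from PR to PD, because a PR scan does not strictly meet the SD definition. That also stands; for that subject the conflict with the text depends on reading PR as at least SD, which the protocol does not say. It does not touch the conflict between cell and footnote, and an earlier SD scan makes the conflict with the text strict.

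Third, a reader might infer that SD is proven to be the intended class. The documents do not go that far. Appendix 1 describes itself as an overview of published criteria that are not reproduced here. The printed cell and the backward-looking SD test point to SD, but what is certain is only that the rules disagree.

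Fourth, the consequences are small: the affected endpoints are exploratory and untested, and the number of affected subjects is unknown and may be zero. The interval shifts cover every possible DCR count and are no forecast for this trial. This limits the severity but does not remove the error. Nor is it detail that can be left to an analysis plan, since the protocol has already fixed the rule and fixed it inconsistently.

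**Conclusion.** The point holds, at low severity. Footnote b cannot work in the rows whose confirmatory scan is PD. It contradicts the printed SD for PR then PD, leaves the SD option for CR then PD unreachable, and conflicts strictly with the text for SD, then unconfirmed PR, then PD.

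The size is 3.2 points of DCR per affected subject, assuming 31 treated subjects; no number of affected subjects is assumed. CBR can move only when the unconfirmed response falls at 23 weeks or later.

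A reader might infer that a fault in the BOR table reaches the primary endpoint or the two-stage decision. It does not, because the dispute lies wholly between two non-response classes. Nor is the 5-week interval at fault. The scan days used here assume on-schedule assessments counted from first dose.

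**What to change.** Keep footnote b as it is for the CR-then-SD row, where it works. Give the CR-then-PD and PR-then-PD rows a new footnote: *SD if at least one scan before progression, 5 weeks or more after first dose, showed SD or better; otherwise PD.* Naming first dose also settles the undefined study entry, and it is the start point that PFS already uses.

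Under this wording every on-schedule first CR or PR followed by PD gives SD. PD remains only where no scan before progression reached 5 weeks, as with an early unscheduled scan. The printed SD for PR then PD can stay with the footnote attached, although printing SD or PD there would be clearer.

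Footnote c has the same wording fault in the CR-then-NE and PR-then-NE rows, where the confirmatory scan is NE. Make the matching change, ending with NE in place of PD.

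A simpler rewording of footnote b for all three rows, testing only whether the first scan came at least 5 weeks after first dose, should be avoided. Take CR on an early scan at day 20 and SD at day 56. The gap is 56 − 20 = 36 days, so the present footnote gives SD, and the SD scan lies 55 days after first dose. The simpler wording would give PD, because the first scan came at 19 days.

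The cost is a text correction in Appendix 1 at the next amendment, carried into the BOR derivation before database lock. No subjects or scans are added.
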